6.2 Visit 2/End of Study Visit

One blood draw will be performed at the first standard of care, post-surgical outpatient follow-up visit. A final adverse event assessment will also be performed at this visit and documented. Any unresolved, oxytocin related adverse events will be followed until resolution. Any adverse events deemed unrelated to oxytocin administration will be considered resolved at this time. Any applicable standard of care interventions to address non-oxytocin related adverse events will be handled as per standard clinical practice. No further contributions to the study will be required after this visit.

6.3 Study Calendar

	Pre-Study	Visit 1	Visit 2/End of Study Visit
Informed consent	X		
Demographics	X		
Medical history	X		
Oxytocin Administration		X	
NAF collection		X	
Adverse event evaluation	X	X	X ^e
Blood Pressure	X	X ^b	
B-HCG^a	X ^a		
Patient Questionnaire		X ^d	
Serum Blood Draw		X	X
Pharmacokinetic Blood Draw		X ^c	
Tissue from On-Study Surgery		X	

a: Only for subjects who are of childbearing potential
b: Blood pressure recordings will be taken prior to oxytocin administration, and approximately 5 minutes post-administration of oxytocin.

CONFIDENTIAL

This material is the property of [name]. Do not disclose or use except as authorized in writing by the study sponsor

c: PKs will be drawn prior to the administration of oxytocin, and then a post-administration PK will be drawn approximately 30 minutes post oxytocin administration.
d: Questionnaire can be administered any time after the subject signs the informed consent, so long as it is captured prior to the administration of oxytocin.e. Adverse events will be recorded at visit 2/End of Study visit, if there are any adverse events that are attributed to oxytocin, they will and must be followed until resolution. All other adverse events that are not attributable to oxytocin will be considered closed out at this visit, and will be followed/addressed via standard of care clinical/medical interventional procedures.

7 Statistical Plan

7.1 Sample Size Consideration

Contralateral breast without disease will serve as the control. In a sample of 40 patients with unilateral disease, we expect 60% of the patients to show significantly altered expression of miRNAs in the diseased breast as compared to the breast without disease for the test to be of clinical relevance. Ideally a detectable difference would be the difference between a null hypothesis of 0% and an alternative of 60% or a second alternative of 35%. Since this study is the first of its kind, we will consider the test to be not clinically relevant if less than 35% of patients show significantly altered expression miRNA in the diseased breast as compared to the breast without disease.

Using a two sample z-test, type I error of 0.05, and a two-sided significance level, a sample size of 40 will have greater than 80% power to detect a difference between a null hypothesis of 35% and an alternative hypothesis of 60%.

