3.1 General Design

We propose a pilot proof of principle study to assess and compare the miR fingerprint (or profile) in NAF, serum, and tissue from patients undergoing a lumpectomy or mastectomy for in situ or invasive breast cancer. As this study is a proof of concept there is no power presented. Other than the collection of NAF, treatment will not vary from the standard of care. The collection of all specimen types will be completed within the regularly scheduled operative time period. The surgery will not be prolonged in any way for specimen collection. Forty patients (20 with DCIS, 20 with invasive breast cancer) will be entered into the study. A total of 5 patients will also undergo pharmacokinetic (PK) draws during the time of surgery to assess the baseline oxytocin level. All other subjects enrolled will be enrolled into the “non-PK” cohort. Patients receiving care at the Breast Surgery Department at Columbia who meet criteria will be offered participation in the study. Patients will answer a brief questionnaire preoperatively. At the time of surgery patients will undergo a blood draw as well as collection of NAF (via prior administration of intranasal oxytocin, gentle massage, aspirator, and breast pump from both breasts). The NAF and blood samples will be sent to the pathology lab for analysis of miR profile. At the completion of the case, the breast tissue will be sent to pathology per routine. Once in pathology, 5 paraffin-embedded slices will be created to evaluate for miR profile. Serum, NAF, and tissue will be analyzed for their miR profile.

Once total RNA is extracted from the biological samples it will be processed to fluorescently label the microRNAs species according to the V2-Human microRNA array (Agilent). MicroRNA profiling will be obtained and analyzed using the gene-spring software analysis package. First, expression and cluster analysis will be performed to identify the microRNA that are expressed in our samples and to classify them accordingly to their expression. Then, the predicted targets of the over/down-regulated microRNAs will be identified using target prediction bioinformatics tools (TargetScan, Miranda and Pictarvert). Finally, statistical studies between over/under-represented microRNAs will be performed.

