4.1 Inclusion Criteria

Patients meeting the following criteria may be included in the study:

- All female patients with DCIS or invasive breast cancer who are scheduled for a lumpectomy or mastectomy and are receiving surgical care from the Breast Surgery Department at Columbia Medical Center.
- Patients diagnosed with unilateral DCIS or invasive breast cancer

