4.2 Exclusion Criteria

Patients meeting the following criteria will be excluded from the study:

- Patients not receiving breast surgery care from the Department of Breast Surgery at Columbia Medical Center.
- Pregnant patients are to be excluded given the risk associated with oxytocin.
- Male patients
- Patients with a prior breast cancer diagnosis
- Patients who have had an adverse reaction to oxytocin

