5.2 Treatment Regimen

The Principal Investigator will administer one spray of intranasal oxytocin, or 4 IU, into each nostril approximately 15-30 minutes before NAF collection. Prior to collection, the nipples will be scrubbed with alcohol swabs to eliminate keratin plugs, breasts will be massaged by the MD investigator for approximately 2 minutes, but no more than approximately 7 minutes. An aspirator will be applied to each breast, and fluid will be collected into capillary tubes. NAF samples will be acquired from study subjects by the MD investigator in the operating room while under anesthesia before the opening incision. The duration of time required to obtain NAF samples will be documented.

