5.6 Prior and Concomitant Therapy

N/A

CONFIDENTIAL

This material is the property of [name]. Do not disclose or use except as authorized in writing by the study sponsor

5.7 *Packaging*

Intranasal oxytocin is packaged into spray containers by the manufacturer (Novartis).

5.8 *Blinding of Study Drug*

N/A. All patients enrolled in the study will receive intranasal oxytocin.

5.9 *Receiving, Storage, Dispensing and Return*

5.9.1 *Receipt of Drug Supplies*

Upon receipt of the of the study treatment supplies, an inventory must be performed and a drug receipt documented by the appropriate research pharmacy personnel accepting the shipment. It is important that the designated study staff counts and verifies that the shipment contains all the items noted in the shipment inventory. Any damaged or unusable study drug in a given shipment (active drug or comparator) will be documented in the study files.

5.9.2 *Storage*

The drug must be refrigerated at 35.6 – 46.4 degrees Fahrenheit, and may be used up to 1 month after opening.

5.9.3 *Dispensing of Study Drug*

The drug will be stored at and dispensed by at the research pharmacy.

5.9.4 *Return or Destruction of Study Drug*

Empty/used oxytocin spray containers will be returned to the research pharmacy. At the completion of the study, there will be a final reconciliation of drug shipped, drug consumed, and drug remaining. This reconciliation will be logged on the drug reconciliation form, signed and dated. Any discrepancies noted will be investigated, resolved, and documented prior to return or destruction of unused study drug. Drug destroyed on site will be documented in the study files.

6 *Study Procedures*

6.1 *Visit 1*

The collection of all specimen types will be completed within the regularly scheduled operative time period. The surgery will not be prolonged in any way for specimen collection. Patients will answer a brief questionnaire preoperatively, after the subject has consented to the trial and prior to administration of oxytocin. Blood pressure will be recorded prior to oxytocin administration and 5 minutes post-administration of oxytocin.

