7.2 Statistical Methods

The primary analysis will be conducted to determine the presence and expression levels of 800 miRNA's among DCIS and invasive breast cancer patients. Based on the resulting profiles, we will determine whether or not its expression for each miRNA from the tumor side differs from that of the normal side.

We will interrogate 800 miRNAs. The vast majority will not be expressed in any sample. A minority will be measurable/detectable in some samples and a smaller minority will be detectable in all samples.

The presence of miRNA can be as follows:

- a. Present in tumor and absent in normal
- b. Present in normal and absent in tumor
- c. Present at high level in tumor and low level in normal
- d. Present at high level in normal side and low level in tumor.

Of these a and c are most important and relevant for our analysis. If even a single miRNA is absent in tumor and present in 30% of cancers or if there is at least one miRNA out of these 800 that is present at low levels in all "normals" and high levels in 30% of tumors that would be a "success". We will dichotomize to low and high levels of miRNA to calculate frequencies and the associated risk estimates and 95% confidence intervals. The comparison of proportions will be performed using two-sample z-tests.

CONFIDENTIAL

This material is the property of [name]. Do not disclose or use except as authorized in writing by the study sponsor

7.3 *Subject Population(s) for Analysis*

Patients diagnosed with DCIS or invasive breast cancer.

8 Safety and Adverse Events

8.1 *Definitions*

Adverse Event

An ***adverse event*** (AE) is any symptom, sign, illness or experience that develops or worsens in severity during the course of the study. Intercurrent illnesses or injuries should be regarded as adverse events. Abnormal results of diagnostic procedures are considered to be adverse events if the abnormality:

- results in study withdrawal
- is associated with a serious adverse event
- is associated with clinical signs or symptoms
- leads to additional treatment or to further diagnostic tests
- is considered by the investigator to be of clinical significance

Serious Adverse Event

Adverse events are classified as serious or non-serious. A ***serious adverse event*** is any AE that is:

- fatal
- life-threatening
- requires or prolongs hospital stay
- results in persistent or significant disability or incapacity
- a congenital anomaly or birth defect
- an important medical event

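### The tumor breast has probably been biopsied before NAF collection and the control breast usually has not, so the 7.2 success statement cannot separate a tumor signal from blood or injury in the duct

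*Combined protocol and SAP*

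**What the plan says.** All references are to the combined protocol and SAP.

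- **Control (7.1).** "Contralateral breast without disease will serve as the control".
- **Entry (4.1, 3.1).** One criterion is "Patients diagnosed with unilateral DCIS or invasive breast cancer". Section 3.1 fixes the split: "Forty patients (20 with DCIS, 20 with invasive breast cancer) will be entered into the study".
- **Timing (5.2).** NAF is collected "in the operating room while under anesthesia before the opening incision". It is the only specimen that the protocol plans to take from both breasts.
- **Exclusions (4.2).** There are five: care at another center, pregnancy, male sex, a reaction to oxytocin, and "Patients with a prior breast cancer diagnosis". None concerns biopsy, time since biopsy or bloody NAF. Section 5.6, "Prior and Concomitant Therapy", is marked not applicable.
- **Success (7.2).** Of four expression patterns, two are called most relevant. The first is "Present in tumor and absent in normal"; the second is a high level in tumor with a low level in normal. One miRNA of 800 is enough. The first success clause reads "If even a single miRNA is absent in tumor and present in 30% of cancers". As worded it contradicts itself; I read it as absent in normal and present in 30% of cancers. The second clause asks for low levels in all normal samples and high levels in 30% of tumors.
- **Other specimens (2, 6.1).** Serum and tissue are profiled too and compared with NAF, but no rule uses them to screen a success miRNA.

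**The concern.** A within-woman control removes everything the two breasts share. It does not remove what differs between them apart from the tumor, and recent instrumentation probably does differ. A diagnosis that already separates DCIS from invasive cancer before surgery implies that tissue was taken from that breast. Bleeding or healing in a duct could then add miRNAs to tumor-side NAF only. They would fit either of the patterns that 7.2 treats as most relevant.

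At stake is what a success would mean. Section 2 gives a screening tool as the goal. A marker of a recent biopsy would not serve women who have not yet had one, and the plan as written has no step that would tell the two apart.

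**Working it through.** **1. The plan's own figure.** The plan gives no contamination rate. Its only power statement is above 80% for 35% versus 60% with 40 patients (7.1). A one-sample z-test reproduces it: Φ[(0.25 − 1.96·√(0.35·0.65/40)) / √(0.60·0.40/40)] = 0.906. Nothing below depends on it.

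**2. Inputs.**
- Pairs: 40 (3.1), or 0.77 × 40 = 30.8, about 31, using the bilateral yield expected in section 2.
- Threshold: 30% (7.2), which is 12 of 40, or 10 of 31 (0.30 × 31 = 9.3, rounded up).
- q: share of women in whom one blood or injury miRNA appears on the tumor side. This is an assumption, shown over a range.
- True tumor effect: none.

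**3. Contaminant never seen on the control side.** P(X ≥ r), X ~ Binomial(n, q):

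| q | 40 pairs, r = 12 | 31 pairs, r = 10 |
|---|---|---|
| 10% | 0.0004 | 0.0006 |
| 15% | 0.012 | 0.012 |
| 20% | 0.088 | 0.075 |
| 30% | 0.559 | 0.458 |
| 40% | 0.929 | 0.857 |

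These are for one given miRNA. If several behave this way, the chance that at least one passes is equal or higher.

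**4. Some background on the control side.** Suppose the requirement of low levels in all normals is applied to every control sample. Let b be the chance that the contaminant is high in a control sample, independent of the other side. The step 3 figure is then multiplied by (1 − b)^n. For q = 30%:

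| b | 40 pairs | 31 pairs |
|---|---|---|
| 1% | 0.559 × 0.669 = 0.37 | 0.458 × 0.732 = 0.34 |
| 2% | 0.559 × 0.446 = 0.25 | 0.458 × 0.535 = 0.25 |
| 5% | 0.559 × 0.129 = 0.07 | 0.458 × 0.204 = 0.09 |

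**5. Does the planned test protect?** Take the two-sample z-test of 7.2 with an assumed 5% on the control side and 5% + 30% = 35% on the tumor side. The pooled rate is 0.20. Power is Φ[(0.30 − 1.96·√(2·0.20·0.80/n)) / √((0.05·0.95 + 0.35·0.65)/n)], which is 0.86 for n = 31 and 0.93 for n = 40. The test finds a real difference between the sides but cannot say what caused it. A multiplicity correction would not change that.

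**The case against.** **The mechanism is inferred.** The documents do not mention biopsy, wire, tracer, dye or blood in NAF. A reader might infer that the plan shows the tumor breast to be biopsied and the control breast untouched. It does not. Sampling of the tumor side is a fair inference from a diagnosis by histology. Same-day wire or dye cannot be inferred at all, and an earlier benign biopsy on the control side is not excluded. That last point dilutes the imbalance without removing it. Nor do the documents show that instrumentation puts miRNAs into NAF.

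**The size is assumed.** A reader might infer from the 56% and 93% figures that a false success is likely. At 10% contamination the chance is negligible, and at 15% it is about 1%. Zero control-side background is also an assumption: 5.2 has both breasts scrubbed, massaged and aspirated. Step 4 shows how much this matters.

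**Some of it may already be captured.** The calendar in 6.3 lists medical history and a questionnaire, whose contents are not shown. It cannot be said that biopsy goes unrecorded, only that no analysis uses it.

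**Serum is not a ready detector.** A reader might expect each woman's serum profile to reveal contaminated NAF. Serum is cell-free and need not carry blood-cell or local healing miRNAs. Section 2 also looks for relationships between NAF and serum, so dropping NAF that resembles serum could remove real signal.

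**It is a pilot.** The primary endpoint in 3.2 is feasible miR analysis, which this does not touch. That stands and limits the weight of the point. The success statement in 7.2 remains exposed.

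**Conclusion.** The point holds as a limit on interpretation. Tumor side and recently instrumented side are probably largely the same breast, and 7.2 would count a qualifying miRNA as a success whether it came from tumor or from blood or injury. The direction is toward false success. The size cannot be taken from the documents: over the assumed range it runs from negligible (about 0.04% at 10% contamination, 40 pairs, no background) to decisive (93% at 40%). At 30% contamination it falls from 56% to 7% as control-side background rises from 0 to 5%. The conclusion rests on two assumptions: that diagnosis involved sampling of the tumor breast, and that such sampling can leave miRNAs in NAF. The documents do not support saying that false success is expected, or that feasibility is compromised. This is a worthwhile, cheap improvement and not a flaw that invalidates the design.

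**What to change.** **Data collection (6.1, 6.3 and the case report form).** Record for each breast the date and type of any earlier biopsy, and any same-day procedure done before NAF collection. Record a visible-blood grade for each NAF sample at collection, because it may not be recoverable later.

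**Analysis (7.2).**
- Pre-specify a sensitivity analysis for any success miRNA that repeats the tumor-versus-normal comparison without pairs containing a visibly blood-stained sample.
- Describe that miRNA's tumor-side rate by time since biopsy. With about 31 pairs this is descriptive only.
- State that a miRNA which does not persist cannot be attributed to tumor. This does not prove it an artifact, since a tumor may itself bleed into a duct. Persistence is also not proof of tumor origin, because a visual grade can miss traces of blood and healing without blood.
- Report comparison with the woman's own serum and tumor tissue profiles as supporting description, not as a condition of success.
- Correct the self-contradictory first success clause.

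**Cost.** A few more form fields per breast, one grade per sample, one extra analysis, and fewer pairs in that analysis. No new procedure is needed.

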1.5 Dose Rationale and Risk/Benefits

Based on prior studies in non-lactating women, we plan to administer one spray (4 IU) per nostril 15-30 minutes before NAF collection. The benefits will be greater NAF yield for miR analysis. The risks include rare anaphylactic reactions, common headache, tachycardia or bradycardia, uncommon arrhythmia, very rare hypertension, common nausea and vomiting, rare rash and allergic dermatitis, and uncommon abnormal uterine contractions. Because of the possibility of abnormal uterine contractions, pregnant women will be excluded in the study. [Frequency: *Very common* (> 1/10); *common* (> 1/100 to < 1/10); *uncommon* (> 1/1000 to < 1/100); *rare* (> 1/10 000 to < 1/1000); *very rare* (< 1/10 000), including isolated cases.]

2 Study Objectives

The main objective of this study is to demonstrate the feasibility of characterizing miR profiles in the NAF, serum and tissue of patients with DCIS or invasive breast cancer. Each set of miRs will be assessed for correlation with tumor presence. Tissue and serum are expected to be acquired from all patients. With the addition of intranasal oxytocin, bilateral NAF collection of adequate volume for analysis is expected from 77% of participants at increased risk for breast cancer.¹⁶

Analysis of the miR profiles will include comparisons among the different biological samples (tissue, serum, NAF) in order to understand their relationships with one another. We hypothesize that cancer subtypes will be identifiable by unique miR fingerprints, with the goal of creating a breast cancer screening tool.

²⁸ Pedersen, Cort A., and David L. Penn. "Oxytocin Treatment of Social Cognitive and Functional Deficits in Schizophrenia - Full Text View - ClinicalTrials.gov." *Oxytocin Treatment of Social Cognitive and Functional Deficits in Schizophrenia - Full Text View - ClinicalTrials.gov*. National Institute of Mental Health, n.d. Web. <<http://clinicaltrials.gov/ct2/show/NCT01394471>>.

²⁹ Guastella, Adam J., Stewart L. Einfeld, Kylie M. Gray, Nicole J. Rinehart, Bruce J. Tonge, Timothy J. Lambert, and Ian B. Hickie. "Intranasal Oxytocin Improves Emotion Recognition for Youth with Autism Spectrum Disorders." *Biological Psychiatry* 67.7 (2010): 692-694.

³⁰ Simeon, D., J. Bartz, H. Hamilton, S. Crystal, A. Braun, S. Ketay, and E. Hollander. "Oxytocin Administration Attenuates Stress Reactivity in Borderline Personality Disorder: A Pilot Study." *Psychoneuroendocrinology* 36.9 (2011): 1418-421.

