Our aim is to first demonstrate proof of principle. We would like to extend our initial trial by 1 year since the NAF volumes were inadequate without pharmacologic enhancement. Specifically, we were able to collect NAF from 13/40 patients, of which 8 were successfully analyzed for miR. To remedy this problem, we propose collecting additional specimens in the setting of intranasal oxytocin. This project will establish a foundation from which future miR analysis may be completed.

3 Study Design

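### Section 7.1 counts and powers all 40 patients, but only women with analysable fluid from both breasts (about 31 on the plan's own figure) can be scored, and no denominator rule covers the rest

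*Combined protocol and SAP*

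**What the plan says.** Section 7.1 takes the unaffected breast as each woman's control and states its target over the whole sample: "In a sample of 40 patients with unilateral disease, we expect 60% of the patients to show significantly altered expression of miRNAs in the diseased" side. A result under 35% of patients is to be read as lacking clinical relevance. The power statement begins "Using a two sample z-test, type I error of 0.05, and a two-sided significance level" and claims that "a sample size of 40 will have greater than 80% power" for 35% against 60%. Section 7.2 compares the tumor side with the normal side for each miRNA and again names two-sample z-tests. Section 7.3 gives the analysis population in one line: "Patients diagnosed with DCIS or invasive breast cancer".

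Section 2 expects tissue and serum from everyone, but "bilateral NAF collection of adequate volume for analysis is expected from 77% of participants at increased risk for breast cancer". Of the earlier phase without oxytocin it reports that "we were able to collect NAF from 13/40 patients, of which 8 were successfully analyzed for miR". Sections 3.1 and 6.1 describe NAF as the only specimen taken from both breasts, and the calendar in 6.3 lists tissue only from the on-study operation. Section 3.1 also says that no power is presented.

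**The concern.** The proportion in 7.1 is built from within-woman comparisons. A woman has no comparison if she yields no fluid, yields it from one breast only, gives too little from either side, or has a sample that fails the assay. The plan expects such losses, since low yield is the reason for adding oxytocin. Yet no section says whether these women are excluded, replaced or left in the count.

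Sections 7.1 and 7.3 put every diagnosed patient in the denominator. A woman with no pair cannot enter the numerator, so in effect she counts as showing no difference. Failure to obtain fluid would then be read as absence of a tumor-normal difference. The same data could fall on either side of the 35% floor depending on a choice made after the results are known.

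**Working it through.** **Inputs.** N = 40, p0 = 0.35, p1 = 0.60, two-sided 0.05 (7.1); bilateral adequate yield 0.77 (section 2); earlier assay success 8/13 (section 2). Assumption: whether a woman can be scored is unrelated to whether her expression is altered.

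**1. The plan's own power figure.** One-sample z-test against a fixed 35%:
Power = Φ[(p1 − p0 − 1.96·√(p0(1−p0)/n)) / √(p1(1−p1)/n)].
- At n = 40: (0.25 − 1.96 × 0.0754)/0.0775 = 1.32, so power is about 91%.
- Exact binomial: the smallest cutoff with upper tail at most 0.025 under 35% is 21/40 (tail 0.017). Power at 60% is 87%.

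Both agree with a claim of more than 80%. The two-sample z-test that 7.1 names does not. With 40 per sample and pooled rate 0.475: (0.25 − 1.96 × √(2 × 0.475 × 0.525/40)) / √((0.2275 + 0.24)/40) = (0.25 − 0.2189)/0.1081 = 0.288, so power is about 61%. The stated power is therefore reproduced only on the one-sample reading.

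**2. Expected pairs.** 40 × 0.77 = 30.8, so about 31 women can be scored and about 9 cannot.

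**3. The 35% floor.** 35% of 31 is 10.85; 35% of 40 is 14.

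| Altered women | Out of 31 | Out of 40 |
|---|---|---|
| 11 | 35.5% | 27.5% |
| 12 | 38.7% | 30.0% |
| 13 | 41.9% | 32.5% |

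Each of these counts clears the floor on one denominator and misses it on the other.

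**4. Unpaired women kept in the denominator.** The 60% alternative becomes 0.60 × 0.77 = 0.462.
- Exact cutoff 21/40: power 26%.
- z-test cutoff 20/40, since (0.50 − 0.35)/0.0754 = 1.99: probability of reaching it 37%.
- Normal-approximation formula: (0.112 − 0.1478)/0.0788 = −0.45, or 32%.

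**5. Unpaired women excluded (n = 31).**
- Normal approximation: (0.25 − 1.96 × 0.0857)/0.0880 = 0.93, or about 82%.
- Exact: cutoff 17/31 (tail 0.019), power 78%.
- Averaged over a random number of pairs, Binomial(40, 0.77): about 82% by normal approximation, 75.6% exact.
- Named two-sample z-test, 31 per sample: (0.25 − 0.2486)/0.1228 = 0.011, or about 50%.

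**6. Pessimistic case (assumption only).** If the earlier 8/13 assay success applied on top of the yield, 40 × 0.77 × 8/13 = 18.95, about 19 pairs. One-sample power with unpaired women excluded would be 49% exact or 62% by normal approximation.

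**The case against.** The strongest reply is that the expected losses do not by themselves defeat the power claim, and this stands. A reader might infer that 77% yield means more than 80% power is not delivered. But 7.1 names a z-test, and in one-sample form it needs 30 women for 80% (81.2% at 30, 79.9% at 29). Since 30/0.77 = 38.96, enrolling 39 would cover that yield, and 40 does. The shortfall with pairs as denominator appears only under exact calculation and is small. The larger power problem is the two-sample wording, which misses 80% at 40 per sample before any pair is lost.

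It is also fair that no sentence tells the analyst to score an unpaired woman as unaltered, and that 7.2 presupposes a result from each side. The diluted figures therefore depend on applying 7.1 and 7.3 as worded. That wording is the only guidance there is, so the gap remains.

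Three further inferences are not supported:
- **19 pairs as the expected number.** The 77% already refers to volume adequate for analysis, and section 2 blames inadequate volumes for the earlier phase. Multiplying by 8/13 may count the same loss twice.
- **One-breast yield of 13%.** Section 1.4 reports 90% with any fluid, but the 13-point gap to 77% also includes bilateral fluid of inadequate volume.
- **A success probability for the 30% rule in 7.2.** One version of that rule also requires low levels in all normal samples, and any one of 800 miRNAs can satisfy it. A single-marker binomial calculation ignores both conditions.

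Finally, the primary endpoint in 3.2 is feasibility and 3.1 disclaims power. That limits how much rests on the power sentence. It does not remove the relevance threshold that 7.1 goes on to set.

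**Conclusion.** The concern holds for the denominator. On the plan's own yield figure about 9 of 40 women will have no pair, and 7.1 and 7.3 as worded leave them in the count. A true 60% is diluted to about 46%, one-sample power against 35% drops to about 26–37%, and 11 to 13 altered women reverse the relevance verdict. With pairs as the denominator, one-sample power is borderline (78% exact, about 82% by normal approximation), so it would be wrong to say that yield alone breaks the power claim.

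These figures assume that scorability is unrelated to outcome and that 77% carries over from women at increased risk to women with cancer, which the documents do not establish. Because a stated threshold can flip on an unwritten choice, the rule should be written before the expression data are examined.

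**What to change.** 1. In 7.1 to 7.3, define the expression-analysis set as women with assay-passing NAF from both breasts. Use it as the denominator for the 35%/60% proportion, and state that women without a pair are not scored as unaltered. For the 30% rule in 7.2, state that the denominator is the tumors with a usable result.
2. Keep all dosed women as the denominator for feasibility (3.2) and fluid sufficiency (3.3). Count no fluid, one-breast fluid, inadequate volume and failed assay as failures there, so that losses stay visible.
3. Restate power at the expected number of pairs and name the test it belongs to: for a one-sample test against 35% at 31 pairs, about 78% exact (about 82% by normal approximation). Correct the two-sample wording in 7.1 and 7.2 at the same time, since that test gives about 61% at 40 per sample and about 50% at 31. Reconcile the result with the statement in 3.1 that no power is presented.
4. Report, as a sensitivity check, the proportion with unscorable women counted as unaltered. If the 19-pair case is shown, label it a pessimistic assumption and keep it out of the protocol text.

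The cost is rewording and one extra table. The stated power becomes less favourable, and the expression result applies only to women who yield analysable fluid from both breasts.

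### Section 7.1 tests the share of patients with altered miRNA against a 35% null, but the plan never defines an altered patient, limits false positives within one, or allows for chance differences between healthy breasts

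*Combined protocol and SAP*

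**What the plan says.** Section 7.1 takes the contralateral breast as control and states: "In a sample of 40 patients with unilateral disease, we expect 60% of the patients to show significantly altered expression of miRNAs". What it counts is patients who "show significantly altered expression of miRNAs in the diseased breast". Below 35% of patients, the test is to be regarded as not clinically relevant. The same 35% is then the null hypothesis and 60% the alternative: "Using a two sample z-test", with "type I error of 0.05, and a two-sided significance level", it is said that "a sample size of 40 will have greater than 80% power to detect a difference".

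Section 7.2 turns to single miRNAs: "We will interrogate 800 miRNAs". Each is compared between the tumor and normal sides, with four patterns listed: (a) tumor only, (b) normal only, (c) higher in tumor, (d) higher in normal. The section warns that most of the 800 will not be expressed in any sample. It has a success rule that a single miRNA can satisfy, with a 30% frequency threshold. On the test it says: "The comparison of proportions will be performed using two-sample z-tests".

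The Statistical Methodology row of the Study Summary describes something else: presence of miRs against a normative reference population, a binomial test, a Benjamini-Hochberg procedure and a ranking by p-value. No false discovery rate is given, and section 7 does not mention the procedure.

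**The concern.** The unit counted in section 7.1 is a patient, so each patient needs a verdict of altered or not. The plan does not say how many miRNAs must differ, by what test or cut, or at what level. The 0.05 in section 7.1 belongs to the cohort-level test. Sections 3.1, 5.2 and 6.1 describe fluid taken from both breasts at one operation and no replicate array, so there is no stated source for a within-patient error estimate either.

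A null of 35% has its stated type I error only if a cohort without any tumor effect would show at most 35% altered patients. That depends on the missing rule. Two healthy breasts will differ in some miRNAs by chance, and the more miRNAs can be tested, the more often at least one will differ. If the rule is settled after the data are seen, the false-positive rate of the sized comparison is settled with it.

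**Working it through.** **The plan's own figure.** Inputs from section 7.1: n = 40, null 0.35, alternative 0.60, two-sided 0.05.

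- One-sample z-test: null SE = √(0.35×0.65/40) = 0.0754; critical share = 0.35 + 1.96×0.0754 = 0.498; SE under the alternative = √(0.60×0.40/40) = 0.0775; power = Φ((0.60 − 0.498)/0.0775) = 0.906.
- Exact one-sample rule, reject at 21 or more of 40: upper-tail size 0.017, power 0.870.
- Two-sample z-test, the one named: power 0.613 with 40 per group; 62 per group would be needed for 80%.

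The claim of more than 80% therefore reproduces as a test of one share against a fixed 35%, not as the named test.

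**Chance rate per patient.** The plan gives neither a per-miRNA level α nor the number m of testable miRNAs, so both are assumptions here, as are the rule that any one miRNA suffices, independence, and the existence of a valid test for each miRNA. With no true difference, P(altered) = 1 − (1 − α)^m.

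| α | m | P(altered by chance) | P(21 or more of 40) |
|---|---|---|---|
| 0.05 | 9 | 37% | 3% |
| 0.05 | 18 | 60% | 88% |
| 0.05 | 20 | 64% | 95% |
| 0.05 | 100 | 99.4% | about 100% |
| 0.01 | 100 | 63% | 94% |
| 0.001 | 100 | 9.5% | about 0 |
| 0.001 | 800 | 55% | 69% |

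At α = 0.05 the marks are crossed at m = ln(0.65)/ln(0.95) = 8.4 and m = ln(0.40)/ln(0.95) = 17.9, that is, from 9 and 18 miRNAs.

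**Correlation.** With equally correlated normal differences at the 5% level, ρ = 0.5 gives 62% at 50 miRNAs (false rejection 92%) and 78% at 100. With ρ = 0.8 the rate is 36% at 100.

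**With within-patient control.** At 0.05/800 = 0.0000625 per miRNA, 1 − (1 − 0.0000625)^800 = 4.9%, about 2 of 40 patients. The chance of reaching even 14 of 40 is then below 0.0001.

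**A paired null.** With no tumor effect the two sides are exchangeable, so tumor-high and normal-high calls are equally likely whatever the number or correlation of miRNAs. In a simulation of 31 pairs and 100 null miRNAs, with a call when the standardised difference exceeded 2.5 in size, 71% of patients were altered by chance, while the mirror-image exact test rejected in about 3%.

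An any-one McNemar test can run out of discordant patients. With a 5% two-sided cut and 100 independent miRNAs, the expected number is 31 × 2 × (0.975^100 − 0.95^100) = 31 × 0.147 = 4.6. At least 6 are needed for p < 0.05 (2 × 0.5^6 = 0.031; with 5 it is 0.0625).

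**The case against.** - **The high chance rates are conditional.** A reader might infer that chance would flag nearly every patient. The documents do not support that. They state neither a 5% level nor an any-one rule, and section 7.2 says most of the 800 miRNAs will not be expressed. The rate runs from under 10% to about 100% over plausible rules. This objection stands, and the figures above are illustrations. It does not rescue 35% as a null, because that value is right or wrong only relative to a rule that is absent.
- **If there is no within-patient test, 1 − 0.95^m models nothing in the plan.** This is fair. The formula shows what follows on the generous assumption that a valid test per miRNA exists. Without one, the endpoint is simply undefined.
- **Multiplicity is addressed.** The Study Summary does name Benjamini-Hochberg. But it works across miRs against a different comparator and does not decide when a patient is altered.
- **The study need not declare relevance without a tumor signal.** A reader might infer that it would. Section 7.1 uses 35% as a floor for non-relevance, and the only success rule is the per-miRNA one in section 7.2. Its second limb (low in all normals, high in 30% of tumors) has a small chance rate with a fixed cut and independent miRNAs: with 31 pairs, at most 0.9% for 100 expressed miRNAs and 6.8% for 800. With a cut chosen from the data it is about 4% and 28%. This stands, but that rule is not the comparison the study is sized on.
- **It is a pilot.** Section 3.2 makes feasibility the primary endpoint, and section 3.1 says no power is presented. That lowers the stakes. Section 7.1 still states a type I error, a power and a relevance mark.

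**Conclusion.** The point holds in this form: the patient-level rule behind the 35% versus 60% comparison is undefined, nothing in section 7 limits false positives within a patient, and the share is tested nowhere in section 7.2, where the named test is unpaired although the breasts are paired. So 35% cannot be read as a no-signal null, and the stated 0.05 is not assured for this comparison.

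The size depends on the assumptions. With any one miRNA at 5% and independence, 9 testable miRNAs bring the chance share above 35% and 18 above 60%, with about 88% false rejection at 18. A strict level or strong correlation lowers this sharply. The undefined rule is certain from the documents; a particular false-positive rate is not.

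**What to change.** In sections 7.1 and 7.2, before the side labels are released to the array analysis:

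1. Fix the list of detectable miRNAs, chosen without regard to side, and a tumor/normal fold-change cut.
2. For each patient, count tumor-high miRNAs (patterns a and c) minus normal-high miRNAs (b and d). Test the sign of this difference across patients with an exact paired sign test. An exact McNemar test of any tumor-high versus any normal-high is an alternative only if the cut is strict enough to leave discordant patients.
3. Report the 35% and 60% marks as descriptive shares only, beside the mirror-image normal-high share.
4. Drop the two-sample z-test for this comparison.
5. Reconcile section 7 with the Study Summary: which comparator, whether Benjamini-Hochberg applies, to what, and at what rate. Reconcile the power statement with section 3.1.
6. Restate the power for the paired test and the bilateral NAF yield expected in section 2: 77% of 40 = 30.8, about 31 pairs. The yield alone lowers the one-sample z-test power from 0.906 to 0.825.

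The cost is plan wording, with no new samples or visits. The restated power may be less favourable, and the list and cut have to be chosen now, since the documents give neither.
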